medication to dispose of any unused study medication in the manner in which they usually dispose of expired medications or offer to have them return the unused study medication to CAVHS. Participants may withdraw from the study at any time. Withdrawal by the participant will be defined as any participant that informs the study team that they do not wish to continue the study medication, do not wish to allow any further collection of data, and do not wish to have any further contact with the study team. If they do so, they will be considered withdrawn voluntarily from the study. We will document the circumstance(s) and reason(s) for participant withdrawal. The PI may also withdraw participants from the study. This may occur in the event of inter-current illness, adverse events, protocol violations, non-compliance, or administrative reasons. We will assist the participant to ensure that appropriate medication is started at the time of withdrawal. We will instruct participants who withdraw (or are withdrawn) from the study to dispose of any unused study medication in the manner in which they usually dispose of expired medications or offer to have them return the unused study medication to CAVHS. Participants withdrawn from the study will not be replaced. To avoid breaking the blind, results of Visit 1 (Month 2) laboratory tests will not be published in CPRS but will be recorded in the Veterans Information Systems and Technology Architecture (VISTA), which is not used by clinicians for lab review. These lab results will be reviewed by Unblinded Personnel.

**Randomization Lab Criteria:** Baseline lab results (TSH, FT4 and lipid profile) will be reviewed prior to randomization by the Investigator or SC. To qualify for randomization, TSH and FT4 must be within normal reference range and LDL must be  $\leq 190$  mg/dL. Normal reference range for TSH: 0.54 – 5.6 mIU/mL. Normal reference range for FT4: 0.47 – 1.41 ng/dL.

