**Study Medication Discontinuation Criteria:** The Unblinded Personnel will notify Blinded Study Personnel (SC) if a participant develops OH or hyperthyroidism. At which point, the SC will be unblinded. Results will be communicated to participants and treating physicians by Unblinded Study Personnel and/or SC. The participant will be followed per protocol (following discontinuation of study medication) unless they decide to withdraw from the study at the time of study medication discontinuation. Lab criteria for study medication discontinuation: (1) TSH  $> 10$  mIU/mL or (2) TSH  $< 0.34$  mIU/mL or (3) FT4  $< 0.47$  ng/mL or (4) FT4  $> 1.41$  ng/mL. Study medication will be discontinued if any of the criteria are met. Unblinded Study Personnel will maintain a document for each participant with the Month 2 lab results. The document details the criteria for study medication discontinuation and process of notification. The document will be stored in the Unblinded Study Personnel binder in the Research Pharmacy office (a locked, private office) inside the Outpatient Pharmacy area (locked, private area). The SC will collect a copy of the document from Unblinded Study Personnel once the participant completes the study. The copy will be maintained in the participant folder in a locked file cabinet in a private office. The PI will not be alerted to study medication discontinuation. She may inadvertently become aware of study medication discontinuation, but she will not be informed of the reason (hypothyroidism or hyperthyroidism at Month 2) in order to maintain the blind through the planned analysis. Study medication may also be discontinued in the case of early termination (participant decision to withdraw, Investigator decision to withdraw or joint decision). In this case, the PI may be alerted to study medication discontinuation and study medication assignment.

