## **Safety Considerations**

Participants randomized to continuing LT4 treatment will continue to face side effects associated with chronic LT4 use, usually side effects indicative of excessive dosage (exogenous hyperthyroidism). Such effects include flushing, sweating, weight loss, tremor, restlessness, excitability, insomnia, angina pain, cardiac arrhythmias, palpitations, tachycardia, diarrhea, muscle cramps, muscle weakness, menstrual irregularities, and heat intolerance. Although, we do not anticipate any side-effects of continuing LT4 for participants who were already taking it as part of their usual care, at the baseline visit we will exclude participants with thyroid function test results suggestive of exogenous hyperthyroidism. We will also exclude patients who were not previously adherent to their LT4 treatment. This is a safety measure to avoid the possibility of developing exogenous hyperthyroidism for a patient who had normal thyroid labs at the baseline visit as a result of not receiving consistent LT4 therapy previously. All participants will have thyroid function tests 6-8 weeks after their initial visit, which is the recommended time to assess the effects of LT4 changes, and at 6 months post-randomization. If hyperthyroidism is confirmed, participants will be required to stop the trial medication and will be referred to their clinicians for treatment.

As with any medication, allergic reactions are a possibility. Allergy to LT4 is extremely rare and very unlikely to occur in patients who have been taking this medication chronically. Participants will have already been taking LT4 prior to enrollment in the study. If assigned to the LT4 group, the participant will continue the pre-study dose of LT4 throughout the study. Participants will be advised to notify the PI or research coordinator if they experience a significant rash, wheezing or other allergy symptoms.

LT4 interacts with the following drugs: anticoagulants, anti-convulsants, anti-arrhythmics, antidiabetics, beta-blockers, antidepressants, sympathomimetics, cardiac glycosides, antineoplastics, nonsteroidal anti-inflammatory drugs, sex hormones, lipid regulating drugs, and general anesthetics. However, it should be noted that interactions are generally weak and have very limited clinical relevance for the treatment of SCH with LT4. If Veterans' LT4-prescribers have concerns about their participation in the RCT, they will be invited to contact the PI.

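### The FT4 stopping limits are printed in ng/mL, but the same numerals are the FT4 reference and entry range in ng/dL: a 100-fold unit error

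*Combined protocol and SAP*

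**What the plan says.** Two adjacent paragraphs of the combined protocol and SAP give FT4 limits.

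- **Randomization Lab Criteria** (entry): "Normal reference range for FT4: 0.47 – 1.41 ng/dL". The entry rule refers to this range: "To qualify for randomization, TSH and FT4 must be within normal reference range".
- **Study Medication Discontinuation Criteria** (stopping): criteria (3) and (4) read "FT4 $< 0.47$ ng/mL or (4) FT4 $> 1.41$ ng/mL". Criteria (1) and (2) are TSH limits. The list is mandatory, and one hit is enough: "Study medication will be discontinued if any of the criteria are met".

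The stopping paragraph also gives the purpose and the consequence of the limits. On purpose: "The Unblinded Personnel will notify Blinded Study Personnel (SC) if a participant develops OH or hyperthyroidism". On consequence: "At which point, the SC will be unblinded". A per-participant file of Month 2 results, held by the unblinded personnel, repeats the rule: "The document details the criteria for study medication discontinuation and process of notification".

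Safety Considerations relies on the same thyroid tests: "If hyperthyroidism is confirmed, participants will be required to stop the trial medication".

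No other part of the document gives an FT4 unit or explains the difference between the two paragraphs.

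**The concern.** The same two numbers appear with units that differ by a factor of 100, so both paragraphs cannot be right. The wrong one is a decision threshold that stops treatment and, when overt hypothyroidism or hyperthyroidism is reported, unblinds the study coordinator.

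The written limits carry more weight here than in most trials, because the plan removes the usual clinical cross-check in order to protect the blind. Month 2 results are kept out of the record that clinicians use and are reviewed by the unblinded personnel, who are research pharmacy staff. The principal investigator, an endocrinologist, is not told of a laboratory-triggered stop. The safety monitor is asked to confirm that the pharmacy follows the protocol, and an audit against the printed text would find correct conduct to be a deviation. The criteria are also restated in the Month 2 file, so the wrong unit may have been carried over. That file is not among the documents, so this is something to check and not a finding.

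**Working it through.** **Inputs**

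- Reference and entry range: 0.47 to 1.41 ng/dL (Randomization Lab Criteria).
- Stops as printed: below 0.47 ng/mL or above 1.41 ng/mL (Study Medication Discontinuation Criteria).
- Conversion: 1 dL = 100 mL, so 1 ng/mL = 100 ng/dL.

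**Step 1. Put the printed stops into the unit of the reference range.**

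- Low stop: 0.47 × 100 = 47 ng/dL.
- High stop: 1.41 × 100 = 141 ng/dL.

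In the other direction, the reference range is 0.47/100 = 0.0047 to 1.41/100 = 0.0141 ng/mL.

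**Step 2. Compare the values that trigger no FT4 stop with the values that allow entry.**

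| Reading of criteria (3) and (4) | No FT4 stop applies (ng/dL) | Entry range (ng/dL) | Overlap |
|---|---|---|---|
| As printed, ng/mL | 47 to 141 | 0.47 to 1.41 | none, since 1.41 < 47 |
| Corrected, ng/dL | 0.47 to 1.41 | 0.47 to 1.41 | identical |

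**Step 3. Size of the gap.**

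- Printed low stop against the lowest eligible value: 47/0.47 = 100.
- Printed low stop against the highest eligible value: 47/1.41 = 33.3.
- Printed high stop against the upper reference limit: 141/1.41 = 100.

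**Step 4. What the literal rule would do.** Any FT4 below 47 ng/dL meets criterion (3). That covers the whole normal range, and also raised values above 1.41 ng/dL up to 47 ng/dL. A participant with a raised FT4 would therefore still be stopped, but under the low-FT4 criterion. Criterion (4), the one meant to detect a high FT4, would do no work.

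**Step 5. Could text conversion explain it?** A lost micro sign can change the prefix of a unit, but it cannot turn dL into mL. The ng/mL unit also appears twice, once in each criterion. The text is current, is not part of an amendment log, and has no redaction at this point.

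No sample size, power, alpha or margin figure depends on this point.

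**The case against.** The strongest reply is that this is a copying slip whose meaning nobody would miss. The correct range stands one paragraph earlier, the numerals match exactly, and the purpose of the limits is stated. Staff who compare a laboratory result in ng/dL with the bare numerals would apply the rule correctly. If anyone did apply it literally, the first Month 2 result would expose the error. This stands, and it is why the point is minor. It does not make the printed rule correct.

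A second reply is that other safeguards remain. The low-TSH stop also detects hyperthyroidism, Safety Considerations does not make FT4 the only trigger, and the investigator can stop study medication on other grounds. This stands too, with one reservation. In the text available, the TSH stops are printed in mIU/mL, whereas the exclusion criterion uses mIU/L. Read as literally as FT4, a TSH stop below 0.34 mIU/mL would be below 0.34 × 1000 = 340 mIU/L. The TSH backup therefore works only if its unit is read by intent. A misread micro sign could account for the TSH unit, since µIU/mL equals mIU/L, but this cannot be settled without the PDF.

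A third reply is that carry-over into the Month 2 file is conjecture. That is fair. It justifies one check and adds nothing to the severity.

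**Conclusion.** The unit in stopping criteria (3) and (4) is wrong as written, by a factor of 100. Read literally, the band of FT4 values free of a stop (47 to 141 ng/dL) shares no value with the entry range (0.47 to 1.41 ng/dL). With ng/dL the two coincide exactly, which leaves little doubt about the intent.

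Severity is minor and confidence is high. The conclusion rests on the unit conversion and on taking ng/dL in the reference range as the intended unit; the matching numerals and the stated purpose of the stops support that. The judgement that the practical effect is small assumes that staff used the intended limits and that the TSH stops are read by their evident meaning. No harm to any participant is claimed.

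**What to change.** In Study Medication Discontinuation Criteria, change ng/mL to ng/dL in criteria (3) and (4), so that the stops read FT4 below 0.47 ng/dL or above 1.41 ng/dL. Confirm that the Month 2 laboratory document held by the unblinded personnel uses ng/dL.

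As a separate check, look at the TSH unit in the PDF in both laboratory paragraphs. If it prints µIU/mL, nothing needs to change. If it does print mIU/mL, change it to mIU/L to agree with the exclusion limit of 10 mIU/L.

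The cost is two unit corrections in the text and one document check, with no added procedures, visits or participants.

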Randomization Scheme: 1:1, a randomized block design will be implemented to ensure group sizes are equal. Block sizes of 2, 4, and 6 will be used. In addition, randomization will be stratified by participant's pre-study dose of LT4.

Blinded Person(s): PI, Co-Investigators (Drs. [name], [name]), Research Coordinator/Study Staff (SC), Participant, participant's other clinicians (routine care), Biostatistician, Safety Monitor

Unblinded Person(s): [name] (Co-Investigator and Research Pharmacist), [name] (Research Staff and Research Pharmacy), [name] (Research Staff and Pharmacist)

Study Medication Blinding Procedure: The brand of LT4 to be used in this study will be Synthroid® tablets of 25 mcg, 50 mcg, and 75 mcg (AbbVie Inc). The study drugs (LT4 and placebo) will be sourced, assembled, and packaged by the CAVHS Research Pharmacy. Over-encapsulation will be achieved using a capsule filler and will ensure that capsules are kept as small as possible for the ease of swallowing (DB capsules gelatin size AA, color: White Opaque, manufacturer: Capsugel).

Study Medication Dosing: Participants will be instructed to start the study medication the day after randomization. The study medication will be taken orally once a day. A two-month supply of study medication will be provided to the participant at (1) Baseline, (2) around the time of Clinic Follow-up 1, and (3) around the time of Telephone Visit 3 (Month 4). Study medication may also be provided (in-person or by mail) at an unscheduled visit for reasons such as loss of study medication or resupply.

Source of Information: CAVHS veterans

Use of Information: Evaluate the feasibility of LT4 discontinuation among veterans with SCH and determine changes in quality-of-life measures, blood lipids and adverse events.

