## **Data Management**

Adequate qualified staff are available for this research. PI is [name]. She is an endocrinology physician and clinician researcher at CAVHS.

Strategic management service will send data via secure VA email with a password-protected database. Data will be stored on VINCI, secure S drive project folder assigned to the PI for this project and, possibly, REDCap. The servers can only be accessed by assigned VA personnel from behind the VA firewall. REDCap is the VA version for research and is not outside the VA protected environment. Additionally, data sets will be sent by encrypted email to the Biostatistician. They will use software on their laptop (non-VA) to complete the planned analysis. These data sets will not include name, date of birth or SSN. The Biostatistician will be hired through an IPA and will complete and maintain all required CAVHS research training and documentation. We will not grant access to the biostatistician until IRB approval of the personnel. They will use the data sets for the approved analysis only. The original data sets will be maintained with the electronic research records behind the VA firewall.

Study personnel will only access the data needed for completion of their work assignments. No study data will be stored on local hard drives. The PI will ensure that access to data is removed for any research staff member that leaves the study or no longer requires the access to the data for completion of work assignment.

The regulatory files will be maintained electronically. The submission documents for the CAVHS Institutional Review Board (IRB) and Research and Development (R&D) Committee will be maintained on IRB Net. No physical logbooks will be generated or kept for this study. All study logs will be maintained electronically on the HSR&D drive assigned to the PI for this study and/or the research file (S: drive) created for the PI of this study. An electronic storage form will be submitted with the initial project submission.

Paper source documents will be created at the study visits. The source documents will be submitted to the CAVHS IRB and R&D Committee for review with the initial project submission. Any updates to the source documents will be submitted to the CAVHS IRB prior to implementation. Paper source documents will be stored in the participant binders in locked file cabinets in the Coordinator's office at CAVHS.

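### The FT4 limits for stopping study medication are printed in ng/mL, 100 times the normal range that carries the same numerals in ng/dL; the TSH unit also needs confirming

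*Combined protocol and SAP*

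**What the plan says.** The Randomization Lab Criteria require a normal TSH and FT4 before randomization and define normal FT4 as follows: "Normal reference range for FT4: 0.47 – 1.41 ng/dL".

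The next paragraph, Study Medication Discontinuation Criteria, lists four laboratory triggers: TSH above 10, TSH below 0.34, FT4 below 0.47 and FT4 above 1.41. Both FT4 limits carry the unit ng/mL. The second is followed directly by the rule that any one trigger is enough: "ng/mL. Study medication will be discontinued if any of the criteria are met". The same paragraph opens by linking notification to a clinical finding: "The Unblinded Personnel will notify Blinded Study Personnel (SC) if a participant develops OH or hyperthyroidism".

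For TSH, the Exclusion Criteria use mIU/L (above 10 excludes). The reference range (0.54 to 5.6) and the stop limits are printed in mIU/mL.

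On who applies the rule, Compliance and Withdrawal says of the Month 2 results: "These lab results will be reviewed by Unblinded Personnel". The list of unblinded persons consists of pharmacy staff, headed by a "Co-Investigator and Research Pharmacist". The discontinuation paragraph adds: "The PI will not be alerted to study medication discontinuation". A document is kept for each participant with the Month 2 results, and of it the plan says: "The document details the criteria for study medication discontinuation and process of notification".

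**The concern.** The same pair of numerals serves as the normal range in one paragraph and as the stop limits in the next, with units that differ by a factor of 100. One of the two must be wrong, and nothing elsewhere in the document corrects it.

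This is a decision threshold in a safety rule for a trial that withdraws levothyroxine from half of its participants, and the paragraph gives no other numerical limits for the step. Followed as printed, the rule would take participants with normal FT4 off study medication at Month 2, and so end the randomized comparison of treatments for them. It would also label a raised FT4 as a low one. That label matters because the Safety Monitor section has hypothyroidism and hyperthyroidism at Month 2 entered in the adverse event log.

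The specialist who would notice such a slip at once is kept out of this step by design. Data Management says of the principal investigator, "She is an endocrinology physician and clinician researcher at CAVHS", but she is not told of these stops. The printed limits therefore need to be usable without interpretation.

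**Working it through.** The plan has no derived figure to reproduce here. The check is a unit conversion.

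**Inputs**
- Normal FT4: 0.47 to 1.41 ng/dL (Randomization Lab Criteria).
- FT4 stop limits as printed: criterion 3, below 0.47 ng/mL; criterion 4, above 1.41 ng/mL (Study Medication Discontinuation Criteria).
- TSH exclusion limit: above 10 mIU/L (Exclusion Criteria).
- TSH reference range 0.54 to 5.6 and stop limits 10 and 0.34, all printed in mIU/mL.
- Conversions: 1 dL = 100 mL, so 1 ng/mL = 100 ng/dL; 1 L = 1000 mL, so 1 mIU/mL = 1000 mIU/L.

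**FT4 limits on one scale**

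| | ng/dL | ng/mL |
|---|---|---|
| Normal, lower end | 0.47 | 0.0047 |
| Normal, upper end | 1.41 | 0.0141 |
| Criterion 3 as printed | 47 | 0.47 |
| Criterion 4 as printed | 141 | 1.41 |

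The printed lower stop limit is 0.47 / 0.0141 = 33.3 times the top of the normal range and 0.47 / 0.0047 = 100 times the bottom.

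**What the printed rule does**
- FT4 of 0.47 to 1.41 ng/dL (normal): below 47 ng/dL, so criterion 3 is met throughout the range and medication stops.
- FT4 above 1.41 and below 47 ng/dL (high): criterion 3, the low limit, is met; criterion 4 is not. For example, 2.0 ng/dL = 0.020 ng/mL, which is below 0.47 and not above 1.41.
- FT4 from 47 to 141 ng/dL: neither FT4 criterion is met.
- FT4 above 141 ng/dL: criterion 4 is met.

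**What the rule does in ng/dL**

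The limits become below 0.47 and above 1.41 ng/dL, exactly the two ends of the normal range. This fits the stated purpose of detecting overt hypothyroidism or hyperthyroidism, so the intended unit is not in doubt.

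**TSH**
- As printed, 10 mIU/mL = 10,000 mIU/L, against 10 mIU/L in the Exclusion Criteria: 10,000 / 10 = 1000-fold.
- The printed reference range of 0.54 to 5.6 mIU/mL equals 540 to 5,600 mIU/L, which cannot be satisfied together with an exclusion above 10 mIU/L.
- If the source reads µIU/mL, then 1 µIU/mL = 0.001 mIU per 0.001 L = 1 mIU/L. The conflict disappears, and the upper stop limit equals the exclusion limit of 10 mIU/L.
- The text reviewed was extracted from a PDF, and µ may have been read as m. A lost µ cannot explain the FT4 discrepancy, where ng/mL appears twice and ng/dL is intact one paragraph earlier.

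**The case against.** The strongest reply is that this is a typographical slip with no route to harm. All four criteria lead to the same action, so a participant with an FT4 of 2.0 ng/dL is stopped under either reading. Taken literally, the rule stops too many people and misses only values from 47 to 141 ng/dL, which are 33 to 100 times the upper normal limit. It would also break down at the first Month 2 result, because it would stop participants for having the normal FT4 that randomization requires. Staff would simply compare numerals with the laboratory report.

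Oversight is also wider than the pharmacy. Results go to participants and treating physicians, and a medically qualified Safety Monitor reviews the event log at least monthly. The TSH discrepancy may come from the PDF reading, and the Month 2 working document has not been seen.

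Much of this stands. The reversed direction changes the label on an event, not the decision to stop. The intended limits are recoverable, and nothing shows that any participant was handled wrongly. The TSH point is only something to confirm.

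It does not make the printed limits correct. The Safety Monitor reviews a log of events, which does not repair a threshold. The same person must also ensure that the pharmacy follows the protocol, and as printed, sensible practice departs from it.

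**Conclusion.** The concern holds. The FT4 stop limits are wrong as written by a factor of exactly 100: 47 and 141 ng/dL where 0.47 and 1.41 ng/dL were meant. Read literally, the whole normal range triggers a stop, and high values up to 47 ng/dL are classed as low. This rests only on the two printed units and involves no outside figure.

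The practical effect is probably small, on the assumption that staff apply the numerals in the laboratory's reported units. Whether the Month 2 document repeats the error cannot be determined from the protocol. Sample size, power and the analysis methods are unaffected.

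The TSH unit is a 1000-fold conflict as printed and no conflict at all if the source reads µIU/mL; that part remains open.

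Because the error sits in a safety rule and is trivial to remove, it should be fixed.

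**What to change.** 1. In Study Medication Discontinuation Criteria, change the unit of both FT4 limits from ng/mL to ng/dL.
2. Check the TSH unit against the source file and the laboratory's reporting unit, then print mIU/L throughout the Exclusion Criteria, Randomization Lab Criteria and Study Medication Discontinuation Criteria.
3. Check that the Month 2 document held by the unblinded personnel carries the same units, and correct it if it does not.

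All numerals stay as they are. The cost is a short correction of unit labels and one document check, with no change to patients, visits or procedures.

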*Compliance and Withdrawal:* We will provide an **IRB-approved pill diary** to all study participants. The study team will assess study medication compliance throughout the study. The pill diary may be reviewed at the follow-up clinic visits. Study medication compliance will be considered good if the participant reports taking study medication 80-100% of the time. **Participants may decide not to continue the study medication (LT4 or placebo) at any time. Additionally, the PI may decide not to continue the study medication for an individual (for example, following lab results). We will assist the participant to ensure that appropriate medication, if any, is started at the time of study medication discontinuation. If this occurs, the participant will be asked if they will continue the study (including follow-up visits, blood collection and study questionnaires) without continuing the study medication. If the participant agrees, they will be followed per protocol. If the participant does not agree, they will be classified as withdrawn from the study. We will document this occurrence, reason for discontinuation of study medication and participant decision to continue participation in the study (visits, blood collection and study questionnaires). Participants may agree to all or some of the study procedures.** We will instruct participants who discontinue the study

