Full details of all adverse events of special interest (new atrial fibrillation, fractures, acute myocardial infarction, stroke, acute coronary syndrome, heart failure, mortality) including the nature of the event, relationship to study drug and outcome will be recorded. Adverse events of special interest will be monitored and followed up until satisfactory resolution or stabilization. All adverse events will be assessed for seriousness. Serious adverse events will also be assessed for causality, expectedness, and severity. This assessment will be carried out by the PI or designated Investigator. If the study demonstrates a convincing pattern of serious adverse events with either LT4 or placebo (LT4 discontinuation), this would be an important endpoint in its own right. If an association of adverse events is noted with either LT4 or placebo allocation, this would require careful consideration as to whether it is ethical and appropriate to continue with the trial. Adverse events will be recorded at all visits and telephone contacts. Participants will be informed of potential adverse events and advised to contact the study team if needed. Adverse events, adverse drug reactions, unexpected adverse reactions, serious adverse reactions, or suspected unexpected serious adverse events will be recorded, notified, assessed, reported, analyzed, and managed in accordance with the Medicines for Human Use (Clinical Trials) Regulations. The PI may withdraw patients from the study and refer them to their clinicians, who would be notified of the participant's study withdrawal, in the event of inter-current illness or adverse events.

A safety monitor will be designated for the project. They will be a CAVHS provider with medical knowledge and training sufficient to enable review of adverse events and identify any safety concerns for the project. A log documenting all adverse events, including hypothyroidism and hyperthyroidism at Month 2, will be maintained on the secure S drive behind the VA firewall by the SC. The safety monitor

will review the log at pre-specified timepoints (at least monthly). They will be blinded to the study medication assignment.

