This project does not have a Data Safety Monitoring Board. It will use a **data and safety monitoring plan** to ensure (1) that the risk/benefit ratio does not change during the study, (2) that all study procedures are followed as written in the protocol and (3) that the confidentiality of research subjects is maintained. The PI or SC will be in touch with RCT participants by telephone at least monthly. Participants' safety (health status and side effects, if any) will be assessed during these calls, during clinic visits and, if necessary, during unscheduled visit/contact. Participants will be evaluated clinically via vital sign measurements and thyroid function blood tests 6-8 weeks post randomization, 6 months post randomization and, if necessary, during unscheduled visit/contact. In addition, responses to quality-of-life questionnaires will be reviewed for possible significant deterioration. Participants' blood lipids will also be assessed at baseline, 6 months post randomization and, if necessary, during unscheduled visit/contact. As described above, the SC will report adverse events and unanticipated problems to the PI or designated Investigator for assessment of relatedness to the study and seriousness. Serious adverse events will also be assessed for causality, expectedness, and severity by the PI or designated Investigator. Adverse events, adverse drug reactions, unexpected adverse reactions, serious adverse reactions, or suspected unexpected serious adverse events will be recorded, notified, assessed, reported, analyzed, and managed in accordance with the Medicines for Human Use (Clinical Trials) Regulations. Adverse events will be reported to the IRB per local policy and regulations. The PI and study staff plan to meet weekly to review all events observed or reported during the study as well as to review the recruitment and enrollment processes. These meetings will have documented meeting notes/minutes that will be disseminated to all study staff. A safety monitor will be designated for the project.

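### The plan blinds the PI to Month 2 thyroid events through the analysis, but the PI's weekly review of all events makes no exception for them

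*Combined protocol and SAP*

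**What the plan says.** The protocol lists as blinded the PI, the other named Co-Investigators, and "Research Coordinator/Study Staff (SC), Participant, participant's other clinicians (routine care), Biostatistician, Safety Monitor". The only investigator listed as unblinded is the research pharmacist; the other unblinded people are pharmacy research staff.

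Compliance and Withdrawal keeps the Month 2 laboratory results out of the record that clinicians use and gives their review to Unblinded Personnel. Study Medication Discontinuation Criteria has those personnel notify the research coordinator (SC) when a participant becomes overtly hypothyroid or hyperthyroid: "At which point, the SC will be unblinded". For the PI it says "The PI will not be alerted to study medication discontinuation". It accepts that the PI may find out by accident that medication was stopped, but then "she will not be informed of the reason (hypothyroidism or hyperthyroidism at Month 2) in order to maintain the blind through the planned analysis".

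The reporting text is general. Safety Considerations describes "A log documenting all adverse events, including hypothyroidism and hyperthyroidism at Month 2", kept by the SC on the S drive and read at least monthly by a Safety Monitor who is blinded to assignment; the Safety Monitor paragraph says the same of the log's content. The data and safety monitoring plan, under Data Management, says "the SC will report adverse events and unanticipated problems to the PI or designated Investigator", and then "The PI and study staff plan to meet weekly to review all events observed or reported during the study". Minutes of those meetings go to all study staff.

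**The concern.** One section withholds a specific fact from the PI until the analysis is done. Another section puts the same fact on the agenda of a weekly meeting that the PI attends. Staff cannot follow both.

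The fact matters because it carries information about the arm. The PI, or a designated Investigator, judges the relatedness and seriousness of adverse events and the causality, expectedness and severity of serious ones. The PI may also withdraw participants, and completion rate by arm is part of the primary feasibility outcome. Someone who knows that a participant became hypothyroid at Month 2 has good reason to suspect placebo when making those later judgements.

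**Working it through.** No figure in the plan is at issue, so the check sets the texts side by side.

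1. **What is withheld, from whom, until when.** The reason for a Month 2 laboratory-driven stop (hypothyroidism or hyperthyroidism), from the PI, until the planned analysis (Study Medication Discontinuation Criteria).
2. **Is it an adverse event under this protocol?** Yes. Both the Safety Monitor paragraph and Safety Considerations name it as content of the adverse event log.
3. **Does it reach a forum that the PI attends?** Yes. The weekly meeting covers every event observed or reported, and the SC, who completes the log, is study staff.
4. **Is there an exception?** None appears in the Safety Monitor paragraph, Safety Considerations or Data Management. The early-termination clause in the discontinuation section widens what the PI may know. The promise to try to keep the research team blinded, under Safety Considerations, concerns unblinding needed for clinical care.
5. **Are the other two routes closed?** They are not shown to be open, but they are not closed either. Event reports may go to a designated Investigator instead of the PI, but the other named Co-Investigators are blinded too. Logs sit on drive space assigned to or created for the PI; the only limit is a general sentence that staff access what their work needs.
6. **What does the event reveal?** Everyone randomized had TSH and FT4 within range at baseline while taking LT4 (Randomization Lab Criteria). One arm continues the same dose and the other stops. New hypothyroidism at 6-8 weeks is therefore more to be expected on placebo. Hyperthyroidism gives no such signal of placebo.
7. **What can that knowledge affect?** It can affect the PI's event assessments and withdrawal decisions, for the rest of follow-up. Willingness and recruitment rate are untouched. The questionnaires are self-administered, so the route into ThyPRO and EQ-5D scores is weak.
8. **Size.** With 50 randomized 1:1, each arm has 50 / 2 = 25. One such event is 1/50 = 2% of the trial, or 1/25 = 4% of its arm. The documents give no expected rate of meeting the Month 2 criteria, so no total follows.

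**The case against.** The best defence is that the discontinuation section is the specific rule and the weekly review the general one, so the specific rule governs. That is a fair reading of intent, but staff working from the monitoring plan would find nothing telling them to hold these events back. A safeguard that depends on that inference should be written down.

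Several stronger readings are tempting, and the documents do not support them.

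- *All three routes deliver the event to the PI.* Only the weekly review does so on its face. Access to the log is expressly granted only to the Safety Monitor, and reporting has the designated-Investigator alternative.
- *The SC is unblinded without need.* That is a judgement. The SC must know of the event to complete the log, and may be the one to communicate results. What can be said is that no SC task is stated to require the treatment assignment, and that the text does not say whether unblinding means the lab result or the assignment.
- *Unscheduled labs breach the same rule.* The rule covers Month 2 only. Compliance and Withdrawal does let the PI stop study medication, with lab results as its example, and does not say which labs. That needs reconciling, but it is not a breach of the Month 2 rule.
- *The adverse event comparison or completion rate is biased.* The planned chi-square test compares event rates, and nothing says that seriousness or causality grades enter it. Participants whose medication is stopped are followed on unless they withdraw, so a Month 2 stop does not itself lower completion.
- *The number affected can be estimated.* Assuming, say, that 5-30% of 25 placebo participants meet a criterion gives 1.25-7.5 people (2.5-15% of 50), but that range has no basis in the documents. Nor can all events be placed in one arm: two of the four criteria point to excess hormone, which LT4 participants could meet.

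It also stands that little blinding is left in the affected participant once results go to the participant and the treating physician. The remaining purpose is to protect the PI's judgement, which is the purpose the protocol itself states.

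**Conclusion.** The point holds in a narrow form. As written, the procedures do not deliver the PI blind that the protocol promises for Month 2 thyroid events: the weekly review of all events conflicts with it directly, and the reporting route and log access contain no exception that would protect it. The exposure is to the PI's seriousness and causality assessments and withdrawal decisions. This is a risk of influence, not a demonstrated bias, and its effect on the quality-of-life scores is limited.

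The conclusion rests on the texts alone and needs no event rate. The one inference is that new hypothyroidism suggests placebo, which follows from the design. The size cannot be put more closely than one participant in 50 per event.

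**What to change.** - In the Safety Monitor paragraph, Safety Considerations and the monitoring plan under Data Management, state that Month 2 thyroid lab events are kept in a restricted part of the log. The PI cannot open it, and its entries are left out of the PI's weekly review and the circulated minutes until the analysis is complete.
- Keep the Safety Monitor's access to these entries, without treatment assignment, so that oversight is not lost.
- Route any required assessment of these events to a named, qualified Investigator other than the PI. The only investigator now listed as unblinded is the research pharmacist, and the documents do not show that this role is qualified to make such assessments. The designation therefore needs a deliberate choice, accepting that whoever is chosen will know of the event.
- State whether the SC learns the lab result only or also the assignment, and limit it to what the SC's tasks require. The protocol already lets Unblinded Personnel communicate results themselves.
- Reconcile Compliance and Withdrawal with Study Medication Discontinuation Criteria on who acts on post-randomization labs.

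The cost is protocol wording, a split log and slightly more work for existing staff. Sample size, visits and laboratory criteria do not change.
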